5.7 Secondary Endpoints

Secondary endpoints are as follows:

- Clinical: Composite of heart failure hospitalization, ventricular tachycardia (VT)/ventricular fibrillation (VF), crossover of treatment and any-cause mortality at 6 months will be assessed. NYHA functional class and quality of life will also be assessed.
- Electrocardiographic: Change in QRS duration between pre-implant and at hospital discharge, and 6 months will be performed. Arrhythmia occurrence (i.e., atrial fibrillation

(AF), nonsustained VT, VT or VF requiring device therapy) will be documented throughout the study period.

- Echocardiographic: Change in left ventricular end-systolic volume index, chamber dimension, and tissue-strain pre-implant, and at 6 months will be performed by readers blinded to treatment allocation.

5.8 Statistics

Geisinger's Biostatistics Core will perform the statistical analyses. The statistician will be responsible for assisting with study design and statistical analysis to understand the role of HOT-CRT in HF patients.

5.8.1 Statistical Analysis Plan

This is a pilot study to collect data and estimate parameters that are needed to design a larger study. Therefore, the sample size is based on estimating the precision of the change in left ventricular ejection fraction (LVEF). If we assume an equal distribution of subjects with LVEF at baseline above or below 35%, then from the BLOCK-HF trial²⁰ we further assume that the standard deviation of change in LVEF at 6 months will be 7.93. With a sample size of 50 patients in each arm, we can estimate the precision of a 95% confidence interval (i.e., half-width) to be 2.25. A sample size of 50 was chosen due to budget limits.

Survival analysis will be conducted between the two randomized groups to assess time-to-event as an endpoint.

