2 ABSTRACT

Despite the great impact Cardiac Resynchronization therapy (CRT) utilizing biventricular pacing (BVP) has had on heart failure patients, one-third of patients do not respond to CRT, and CRT may result in worsening heart failure and increased mortality in some patients. We hypothesize that in patients with heart failure (HF) eligible for CRT as part of routine standard-of-care based on accepted Class I or Class II indications, His-Purkinje conduction system pacing (HPCSP)-optimized trial of CRT (HOT-CRT) may not only be safely achieved but will also be associated with superior echocardiographic and clinical outcomes compared to conventional BVP during CRT. We aim to determine the overall rate of successful HOT-CRT at the time of implant of CRT in a pilot study, collecting data in BVP and HOT-CRT on acute and mid-term outcomes at Geisinger. Primary outcomes include freedom from major complications and change in left ventricular ejection fraction (LVEF) at 6 months. To compare the effectiveness of HOT-CRT versus traditional CRT in patients with heart failure, patients will be randomized to either HOT-CRT or BVP and will remain blinded to their treatment allocation. Treating physicians will be aware of assignment in order to facilitate routine device follow-up. Echocardiographic evaluation will also be performed in a blinded manner. Crossover is permitted between treatment group allocation as follows: (1) If CS lead (BVP) cannot be placed due to difficult cannulation of the CS, limited branches at the posterolateral or lateral wall, or phrenic nerve capture, patients may then crossover to HOT-CRT. All efforts will be made to achieve CRT using CS lead. (2) HOT-CRT patients may crossover if HPCSP lead cannot be positioned with adequate stability and reasonable pacing output and acceptable electrical resynchronization cannot be achieved. Echocardiographic response to CRT (improvement in left ventricular ejection fraction) and a combination of clinical, electrocardiographic, and echocardiographic endpoints will be prospectively studied. Any complications will also be assessed prospectively, both acutely and throughout the study period.

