3.1 Hypothesis

We hypothesize that:

1. in patients with advanced heart failure and evidence of intraventricular conduction disease who meet criteria for CRT, HOT-CRT may be safely achieved and,
2. HOT-CRT will be associated with superior echocardiographic and clinical outcomes compared to conventional biventricular pacing (BVP) during CRT.

3.2 Specific Aim 1

To determine the overall rate of successful HOT-CRT at the time of implant of CRT. Patients randomized to HOT-CRT but who cannot be successfully implanted with a HPCSP lead will crossover to traditional coronary sinus (CS) lead position.

3.3 Specific Aim 2

To perform a pilot study to collect data in BVP and HOT-CRT on acute and mid-term outcomes at Geisinger. Acute outcomes include change in QRS duration pre-and post-pacing (degree of QRS narrowing) and incidence of major periprocedural complications (pericardial tamponade, need for lead revision, etc.). Mid-term outcomes include echocardiographic response at 6 months along with a composite clinical outcome of heart failure hospitalization, ventricular arrhythmias, crossover, and all-cause mortality.

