5 STUDY DESIGN

5.1 Description

This is a randomized, prospective, single-blinded trial. Patients will be randomized to HOT-CRT versus BVP and will remain blinded to their treatment allocation. Both treatment options use standard-of-care, FDA-approved devices. The distinction is only in the allocation toward HOT-CRT and BVP. Treating physicians will be aware of assignment in order to facilitate routine device follow-up. Echocardiographic evaluation will also be performed in a blinded manner. Study physicians with the role of completing this evaluation will be blinded to lead placement.

Crossover is permitted between treatment group allocation if:

- CS lead (BVP) cannot be placed due to difficult cannulation of the CS, limited branches at the posterolateral or lateral wall, or phrenic nerve capture. These patients may then crossover to HOT-CRT. All efforts will be made to achieve CRT using CS lead.
- HOT-CRT patients may crossover if HPCSP lead cannot be positioned with adequate stability and reasonable pacing output and acceptable electrical resynchronization cannot be achieved.

Implant procedure will be per routine percutaneous access, as is standard for pacemaker and implantable cardioverter defibrillators (ICDs). All patients will receive FDA-approved cardiac resynchronization therapy pacemaker or defibrillator device, as per standard of care outlined for the patient.

Follow-up will be performed at 2 weeks post-implant for incision check and device interrogation, as is standard of care. In addition, routine device and clinical follow-up will be scheduled at 3, and 6 months, with remote device monitoring between scheduled visits, as needed.

Electrocardiography (i.e., ECG) will be performed pre-implant, prior to hospital discharge, and at 3- and 6-months post-discharge, as is standard of care. Echocardiography will be performed pre-implant, at 6 months to evaluate for change in left ventricular ejection fraction (LVEF), chamber dimension, and wall motion with strain imaging as is standard of care in the treatment of patients with advanced heart failure. NYHA functional class and quality of life, as measured

by the Kansas City Cardiomyopathy Questionnaire (KCCQ) and the EuroQoL 5D (EQ-5D), will be assessed pre-implant and at 6 months.

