5.2.1 Approximate Number of Subjects

Approximately 100 Geisinger subjects will participate in this study; approximately 50 in the intervention arm, and approximately 50 in the control arm.

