5.5.1 Participant Withdrawal

Subjects will be free to withdraw from the study at any time by notifying the study team in writing. If the subject withdraws, no further data will be collected after that timepoint unless needed for safety reporting.

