5.8.2 Statistical Power and Sample Size Considerations

Analysis will follow the “intent-to-treat” principle. That is, subjects will be analyzed based on their randomization allocation. A small number of patients might cross-over into the other arm so we will complete a secondary analysis using the per-protocol principle where subjects are analyzed based on their final treatment allocation. Data will be fully described using mean and standard deviation or median and inter-quartile range for continuous measures, and frequency and percentage for categorical variables. Baseline variables will be summarized by randomization arm to assess for balance. Any imbalance will be adjusted for in the estimation of the parameters of interest. Successful placement (Aim 1) will be summarized in the HOT-CRT group among those randomized to this group. The percentage and 95% confidence interval will be estimated. A logistic regression model will be fit to identify baseline factors that associate with success. The primary endpoint in Aim 2, change in LVEF, will be estimated along with the

standard deviation and 95% confidence interval. The difference in change between the randomization arms will also be estimated. No formal statistical inferences will be conducted in this study. Deliverables

Pilot study deliverables will be to establish feasibility, collect preliminary data, and further develop and refine infrastructure to test hypothesis(es) in a fully powered trial. We anticipate being able to identify specific clinical and health care utilizations endpoints during the pilot trial, which will be important to further investigate in a larger, powered trial. We hope to publish our findings and add to the generalizable knowledge to inform physicians, policy-makers, and the healthcare community of real-world outcomes.

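### Is the stated 95% half-width of 2.25 misleading because it describes one arm, not the HOT-CRT versus BVP difference?

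*Combined protocol and SAP*

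**What the plan says.** Section 5.8.1 describes a pilot meant to supply the parameters for designing a larger trial. Its sample size rests on the precision of the change in LVEF, not on power. Taking an SD of 7.93 for the 6-month change from a cited trial, with 50 patients per arm, it says "we can estimate the precision of a 95% confidence interval (i.e., half-width) to be 2.25". It adds that 50 was set by the budget. Section 5.2.1 gives the enrolment as "approximately 50 in the intervention arm, and approximately 50 in the control arm".

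Section 5.8.2 says the change in LVEF will be estimated with its SD and 95% confidence interval. The next sentence reads "The difference in change between the randomization arms will also be estimated". On covariates, it says "Any imbalance will be adjusted for in the estimation of the parameters of interest". It then rules out formal statistical inference and leaves hypothesis testing to a fully powered trial.

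The aims are worded comparatively. The abstract says "To compare the effectiveness of HOT-CRT versus traditional CRT in patients with heart failure, patients will be randomized", and section 3.1 hypothesizes that "HOT-CRT will be associated with superior echocardiographic and clinical outcomes" relative to conventional BVP. Both arms are actively treated: "All patients will receive FDA-approved cardiac resynchronization therapy pacemaker or defibrillator device" (section 5.1).

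**The concern.** Because every patient receives CRT, the LVEF change within one arm mixes any specific benefit of HOT-CRT with the benefit of resynchronization in general. Only the difference between arms isolates the former, and it is what the abstract and section 3.1 are about. Yet the only precision in the plan is a single number with no explicit statement of whether it belongs to one arm or to the difference. A reader who took 2.25 as the precision for HOT-CRT versus BVP would think the comparison tighter than it is.

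The sentence on the difference adds to the doubt, since the interval is named in the sentence before it and not in it. Read strictly, the plan could be met by a point estimate of the difference alone. The observed difference may inform the design of the later trial, so its uncertainty matters.

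The figure also assumes that all 50 patients per arm have a 6-month echocardiogram. No allowance is stated, although section 5.5.1 says "If the subject withdraws, no further data will be collected after that timepoint unless needed for safety reporting".

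**Working it through.** **Inputs.** SD of change 7.93, 50 per arm and 95% confidence (read as two-sided), all from 5.8.1. The SD is the plan's own assumption and cannot be checked here. It is applied to both arms.

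**1. Reproduce the stated figure (mean change within one arm).**
Half-width = t(0.975, 49) × SD/√n = 2.0096 × 7.93/√50 = 2.0096 × 1.1215 = **2.254**, which rounds to the stated 2.25.

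**2. Try other readings.**

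| Reading | Half-width |
|---|---|
| Within arm, normal approximation | 2.198 |
| All 100 patients pooled, t | 1.573 |
| Difference between arms, t (98 df) | 3.147 |
| Difference between arms, normal approximation | 3.109 |

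None of these gives 2.25. The stated figure is the per-arm t interval with all 50 patients measured.

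**3. Half-width for the unadjusted difference.**
t(0.975, 98) × SD × √(2/n) = 1.9845 × 7.93 × √(2/50) = 1.9845 × 1.586 = **3.147**, or about 3.15.
Ratio to the per-arm figure: 3.147/2.254 = 1.397, so about 40% wider.

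**4. Patients needed for 2.25 on the unadjusted difference.**
Normal approximation: n = 2 × (1.96 × 7.93/2.25)² = 95.4, so 96 per arm. With the t quantile, 97 per arm gives 2.246, just under 2.25. This is nearly double the planned size, in a study whose size was fixed by budget.

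**5. Does the text attach 2.25 to the wrong quantity?** Section 5.8.1 speaks of the change in LVEF with 50 patients in each arm. Section 5.8.2 uses one term for the change and another for the difference in change between arms. On that vocabulary 2.25 belongs to the change, and step 1 confirms that this is how it was calculated. The text and the arithmetic agree.

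**6. Does anything depend on 2.25?** The documents contain no success criterion, stopping rule or go/no-go threshold tied to this half-width. Replacing it by 3.15, or printing both, would not alter the number enrolled, the endpoint, the visits or the estimates.

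**The case for a change.** The best case for a change is that confidence intervals are estimation, not testing, so disclaiming formal inference does not excuse leaving one out. The plan already names intervals for placement success and for LVEF change. The randomized contrast on the primary clinical endpoint deserves at least as much, and a pilot difference is uncertain enough that reporting it bare would be unwise. Labelling 2.25, printing 3.15 and naming the interval would take two sentences and cost nothing.

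Much of this stands. The label is missing, 3.15 is not printed, and the sentence on the difference is ambiguous. But ambiguity is not a planned omission: the word *also*, directly after a sentence that names a 95% interval, can naturally carry the interval over. A biostatistics group estimating a two-arm difference would produce its interval by default.

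Three further arguments add little:

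- **Comparing two within-arm intervals.** At these inputs they separate only when the arms differ by 2 × 2.254 = 4.51 points, against 3.15 for the interval on the difference. This is true, but the plan nowhere proposes comparing the arms that way.
- **Missing echocardiograms.** The documents give no rate. If 10% or 20% were missing (assumed; 45 or 40 measured per arm), the per-arm half-width would be 2.38 or 2.54 and that for the difference 3.32 or 3.53. These are modest shifts, and an allowance could not raise an n set by budget.
- **Covariate adjustment.** It could bring 3.15 down, but the documents give no correlation from which to say by how much.

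**Conclusion.** No change to the plan is needed. The half-width of 2.25 is right for the mean LVEF change within one arm. For a pilot that is to supply planning parameters, precision of the per-arm change is a defensible basis for the sample size. What is missing is detail: an explicit label, a second half-width of about 3.15 that follows from the printed SD and n, and the word interval in one sentence. Analysts would fill these gaps sensibly, and the conduct and results of the study would be the same.

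Readers should not take 2.25 as the precision of HOT-CRT versus BVP; the unadjusted figure is about 40% larger. That figure assumes an SD of 7.93 in both arms, 50 measured patients per arm and no covariate adjustment. The conclusion would differ if a decision rule or a formal comparison rested on 2.25, but the documents contain neither.

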5.8.2 Statistical Power and Sample Size Considerations

Analysis will follow the “intent-to-treat” principle. That is, subjects will be analyzed based on their randomization allocation. A small number of patients might cross-over into the other arm so we will complete a secondary analysis using the per-protocol principle where subjects are analyzed based on their final treatment allocation. Data will be fully described using mean and standard deviation or median and inter-quartile range for continuous measures, and frequency and percentage for categorical variables. Baseline variables will be summarized by randomization arm to assess for balance. Any imbalance will be adjusted for in the estimation of the parameters of interest. Successful placement (Aim 1) will be summarized in the HOT-CRT group among those randomized to this group. The percentage and 95% confidence interval will be estimated. A logistic regression model will be fit to identify baseline factors that associate with success. The primary endpoint in Aim 2, change in LVEF, will be estimated along with the

standard deviation and 95% confidence interval. The difference in change between the randomization arms will also be estimated. No formal statistical inferences will be conducted in this study. Deliverables

Pilot study deliverables will be to establish feasibility, collect preliminary data, and further develop and refine infrastructure to test hypothesis(es) in a fully powered trial. We anticipate being able to identify specific clinical and health care utilizations endpoints during the pilot trial, which will be important to further investigate in a larger, powered trial. We hope to publish our findings and add to the generalizable knowledge to inform physicians, policy-makers, and the healthcare community of real-world outcomes.

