The primary clinical endpoint for the study (Aim 2) is change in left ventricular ejection fraction at 6 months. The primary safety endpoint (Aim 1) – freedom from major complications such as pericardial tamponade or need for CRT lead revision.

Secondary endpoints are as follows:

- Clinical: Composite of heart failure hospitalization, ventricular tachycardia (VT)/ventricular fibrillation (VF), crossover of treatment and any-cause mortality at 6 months will be assessed. NYHA functional class and quality of life will also be assessed.
- Electrocardiographic: Change in QRS duration between pre-implant and at hospital discharge, and 6 months will be performed. Arrhythmia occurrence (i.e., atrial fibrillation (AF), nonsustained VT, VT or VF requiring device therapy) will be documented throughout the study period.
- Echocardiographic: Change in left ventricular end-systolic volume index, chamber dimension, and tissue-strain pre-implant, and at 6 months will be performed by readers blinded to treatment allocation.

Regarding primary complication endpoints, complications will be assessed prospectively both acutely and throughout the study period, including:

- Procedure-related: pneumothorax, perforation, pericardial effusion, or hemorrhage
- System-related: implant site hematoma, implant site infection
- Lead-related: lead dislodgement, lead fracture, inability to pace due to high threshold, phrenic capture

Patients will be allocated to HOT-CRT or standard BVP (CS lead) prior to implant procedure. Randomization will be performed by the assigned biostatistician and use a randomly permuted block design. Blocks of size 2 and 4 will be randomly generated. Randomization will be stratified by LBBB and non-LBBB and clinical site.

Chart review will be performed for each enrolled patient upon study completion. The following events/data points will be collected to perform a survival analysis curve between the two randomized groups:

- Date of death and cause of death

- Heart failure hospitalization (HFH), date of HFH, and number of HFHs
- Atrial and ventricular arrhythmias as per device log
- Complications (i.e., lead revision, infection, device replacement, etc.)
- Last encounter date
- Last withdrawal date

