5.9 Data Management

5.9.1 Data Collection and Storage

Only IRB-approved study staff will have access to data collected for this research. Electronic data will be stored on Geisinger's secure network. Any hard copy data will be secured in a locked area. The following data, including relevant dates, will be collected:

- Names
- Medical record number
- Date of birth/date of death
- Information relevant to all encounters, admissions/discharges, clinical procedures, medications administered, problem list entries, device interrogations and lab values
- Baseline demographic variables of patients (age, sex, ethnicity, tobacco use, comorbidities)
- Clinical outcomes and procedural related complications

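### The LVEF arm difference has no named model, and an undefined imbalance rule settles its covariates only after the baseline data are seen

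*Combined protocol and SAP*

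**What the plan says.** Change in LVEF at 6 months is the primary clinical endpoint (5.6). Section 5.8.2 promises the change with its SD and 95% confidence interval, then adds: "The difference in change between the randomization arms will also be estimated". No estimator or model is given for that difference; the only regression named in the section is a logistic model for implant success.

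Covariates are covered by two sentences: "Baseline variables will be summarized by randomization arm to assess for balance", followed by "Any imbalance will be adjusted for in the estimation of the parameters of interest". Imbalance is not defined, and neither the candidate variables nor the method of adjustment is listed.

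On design, section 5.1 states "Randomization will be stratified by LBBB and non-LBBB and clinical site", and 5.5 repeats this. Nothing in the document carries those factors, or baseline LVEF, into the analysis. The stated scope is limited: 5.8.1 says "This is a pilot study to collect data and estimate parameters that are needed to design a larger study", and 5.8.2 says "No formal statistical inferences will be conducted in this study".

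**The concern.** Under this rule the covariate set is fixed by chance baseline differences and an unstated threshold rather than by prognostic value. Baseline LVEF, the obvious covariate for a change in LVEF, may or may not be used. LBBB stratum and site are kept close to balance by the stratified blocks, so a rule triggered by imbalance tends to leave out the factors the design singled out.

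The abstract gives the reason for randomizing: "To compare the effectiveness of HOT-CRT versus traditional CRT in patients with heart failure, patients will be randomized to either HOT-CRT or BVP". The arm difference is the output that makes this comparison. As the text stands, two analysts could both follow it on the same data and report different differences.

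**Working it through.** **Inputs from the plan.** SD of change 7.93 and 50 per arm (5.8.1); strata LBBB/non-LBBB by site, blocks of 2 and 4 (5.1, 5.5); three sites (5.3); LVEF capped at entry at 35% or 50% depending on the criterion (5.2.2).

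**Assumed, because the plan gives no value.** Baseline to 6-month correlation r from 0.3 to 0.7, and SD ratio k (6-month/baseline) from 1 to 1.4. A ratio above 1 is plausible because LVEF is capped at entry but not at 6 months. With SD of change held at 7.93, this grid implies a baseline SD of 7.93/√(1+k²−2rk), or 5.4 to 10.2.

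**1. The plan's own figure.** t(0.975, 49) × 7.93/√50 = 2.254. This reproduces the stated 2.25, which is a single-arm half-width.

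**2. Arm difference, unadjusted.** t(0.975, 98) × 7.93 × √(2/50) = 3.147.

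**3. Arm difference, adjusted for baseline LVEF.** The variance factor is f = k²(1−r²)/(1+k²−2rk), and the half-width is 3.147√f. For example, r=0.5 and k=1 give f = 0.75/1 = 0.750 and 3.147 × 0.866 = 2.73.

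| r | k=1 | k=1.2 | k=1.4 |
|---|---|---|---|
| 0.3 | 2.54 | 2.75 | 2.89 |
| 0.5 | 2.73 | 2.94 | 3.06 |
| 0.7 | 2.90 | 3.09 | 3.15 |

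The gain over unadjusted runs from 0.61 points down to 0.00.

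**4. How often the rule selects each factor.** For an unstratified variable the standard error of the SMD is √(2/50) = 0.20, so P(|SMD|>0.1) = 2(1−Φ(0.5)) = 0.62. A simulation gives the rest: 3,000 trials per setting, N=100, no true effect, no missing data. It assumes sites at 40/40/20, 50% LBBB, and ten other baseline variables drawn as independent normals.

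| Reading of imbalance | Baseline LVEF | LBBB | Site |
|---|---|---|---|
| p<0.05 | 5% | 0% | 0% |
| p<0.10 | 10% | 0% | 0% |
| \|SMD\|>0.1 | 62% | 1% | 6% |
| any nonzero difference | 100% | 85% | 93% |

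**5. How far the estimate moves within one trial.** Over all four readings, maximum minus minimum has a median of 0.41 to 0.68 points (90th percentile 0.89 to 1.45) when the ten other variables are not prognostic. If they jointly explain 20% of residual variance (assumed), the median is 0.65 to 0.84. Between the |SMD|>0.1 and literal readings alone, the median is 0.11 to 0.18 (90th percentile 0.31 to 0.52), against a standard error of about 1.6 for the unadjusted difference.

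**6. Precision of the rule against the prespecified model** (arm, baseline LVEF, LBBB, site), as mean half-width:

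| Ten others | r, k | p<0.05 | \|SMD\|>0.1 | Literal | Prespecified |
|---|---|---|---|---|---|
| not prognostic | 0.5, 1 | 3.17 | 3.06 | 2.90 | 2.74 |
| not prognostic | 0.7, 1.4 | 3.18 | 3.32 | 3.34 | 3.15 |
| explain 20% | 0.5, 1 | 3.16 | 2.87 | 2.60 | 2.74 |
| explain 20% | 0.5, 1.4 | 3.17 | 3.06 | 2.90 | 3.07 |
| explain 20% | 0.7, 1.4 | 3.17 | 3.12 | 2.99 | 3.16 |

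With non-prognostic extras, every reading is wider than the prespecified model. With prognostic extras, five of the nine rule entries are narrower. The empirical standard error agrees: at r=0.5, k=1 it is 1.33 (|SMD|>0.1) and 1.32 (literal) against 1.39 for the prespecified model.

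**7. Validity.** With non-prognostic extras, coverage under the rule was 94.4% to 96.0%, and mean estimates lay within 0.04 of zero.

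**8. Omitting a stratifier.** The simulation gave LBBB and site no prognostic effect. If LBBB shifted the change by g points with 60% LBBB (both assumed), the within-stratum SD would be √(7.93² − 0.24g²). For g = 4 and 6 the half-width becomes 3.05 and 2.92 instead of 3.15.

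**The case against.** The strongest reply is that little rides on this. The study is an estimation-only pilot with no test of the arm difference. Section 5.8.1 sizes it on single-arm precision, and 5.8.2 attaches the SD and confidence interval to the change itself, with no interval promised for the difference. The within-arm SD that would size a later trial is untouched. All of that stands, and it limits the severity.

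A second reply is that the spread over four readings is close to a worst case. Significance-test readings sit badly with a plan that disclaims formal inference and speaks of any imbalance at all; the two readings nearest the text differ by only 0.1 to 0.2 points. This also stands, although the wording does not rule the other readings out.

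Third, a reader might infer that the rule loses precision compared with a prespecified model. The documents do not support that as a general claim. BNP, QRS duration, NYHA class and walk distance may well be prognostic, and then the broader readings can beat a model limited to baseline LVEF and the strata.

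Fourth, a reader might infer that LBBB and site are left to chance. Stratified blocks hold them close to balance, so a threshold reading omits them almost systematically.

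None of these replies supplies the missing definition. The text permits a baseline-adjusted model but does not commit to one.

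**Conclusion.** The point holds in a modest form. The plan names no model for the arm difference, and its covariate rule leaves the choice open until the data are seen. The consequence is an estimate that depends on the analyst's reading: a median of 0.4 to 0.7 LVEF points across four readings (0.65 to 0.84 if other covariates are prognostic), and 0.1 to 0.2 between the two most natural ones.

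A reader might go further and infer a biased estimate or invalid intervals. The documents do not support that: arms are randomized, the simulated estimates centre on zero and coverage is close to nominal.

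The benefit of baseline adjustment over no adjustment is 0 to 0.6 points of half-width, resting on an assumed r and SD ratio. Its benefit over the imbalance rule has no fixed sign, since that turns on how prognostic the other variables are. The selection rates and spreads also rest on the assumed site mix, LBBB share and ten independent covariates. The absence of a model and of a definition rests on the text alone.

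**What to change.** In 5.8.2, replace the imbalance rule with one prespecified linear model for 6-month LVEF (or change in LVEF, which gives the same arm effect once baseline is in the model) on randomized arm, baseline LVEF, LBBB stratum and site. Add any other covariates judged prognostic, named before the data are seen; this also protects against the case in which the broader readings would be more precise. Report the adjusted difference with its 95% confidence interval and the residual SD. Keep the within-arm mean change, SD and interval as planned. Keep the baseline table descriptive, and label any imbalance-driven adjustment as a sensitivity analysis.

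The cost is two or three sentences. Baseline LVEF, LBBB status and site are already collected. The core model spends 4 degrees of freedom (1 baseline, 1 LBBB, 2 for three sites), leaving 100 − 2 − 4 = 94. Where adjustment brings no gain it costs about 0.02 points of half-width (3.15 against 3.13 simulated at r=0.7, SD ratio 1.4).
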